**Figure 8.1-8-2 Study Flowchart**

## 8.2 ALLOCATION AND BLINDING

### 8.2.1 Treatment Allocation

Subjects will be randomly assigned to the CORI navigational or conventional manual instrumentation groups according to a balanced randomization procedure using a 1:1 allocation ratio. To ensure balanced group assignment within each investigational site, a block (by investigational site) randomization schedule will be generated. Only sites will be included that are willing to perform both, CORI Navigated and conventional instrumentation UKA procedures. Subjects who satisfy all inclusion and exclusion criteria will be randomized in a 1:1 randomization allocation ratio. The block size should be sufficiently small to allow approximately equal allocation of subjects in each group should the study be terminated prematurely whilst also being large enough so as the next treatment cannot be guessed.

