### 10.1 GENERAL

S+N's Global Biostatistics group will conduct the statistical analysis for this study. Unless otherwise stated, all significance tests and hypothesis testing will be two-sided, performed at the 5% significance level. Resulting p-values will be quoted and 95% two-sided confidence intervals will be generated where appropriate. Where data summaries are specified, categorical and ordinal variables will be summarized with frequencies and percentages. Continuous variables will be summarized with the following summary statistics: the number of observations, mean, median, standard deviation, minimum and maximum values.

All statistical comparisons of data will describe the test statistic used as well as its distributional assumptions. For continuous variables, in an event of marked deviation from normality assumption, a commensurate non-parametric test would be used as an alternative thereby eliminating the possibility of violation of normality assumptions. All analyses will be performed using SAS version 9.3 (or a later version).

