### 10.4 EFFECTIVENESS ANALYSIS

#### 10.4.1 Analysis of Primary Endpoint

##### Leg alignment

##### CONFIDENTIAL AND PROPRIETARY

This document contains information that is confidential and proprietary to Smith & Nephew PLC and Smith & Nephew, Inc. and is intended for use only by Smith+Nephew and its manufacturer. It shall not be reproduced or copied in whole or in part, nor shall the contents be disclosed by any means without prior written permission from Smith+Nephew, nor shall anyone make any use of it that is contrary to the expressed or implied wishes of Smith+Nephew.

TMP-CD-05-01 Clinical Protocol - Device - Revision D; SOP-CD-05 Clinical Protocol

Clinical Protocol	Study Number: CORI.2019.06
A Prospective, Multi-center, Randomized Controlled Study to Evaluate the Safety and Effectiveness of REAL INTELLIGENCE™ CORI™ in unicondylar knee arthroplasty (UKA) Procedure	Version: 4.0-Master, 07 Sep 2022
	Page: 79 of 167

The primary endpoint, the proportion of knees achieving post-operative leg alignment, defined as  $\pm 3^\circ$  from the target (pre-operative planned leg alignment) assessed at the 6 weeks study visit in CORI UKA ( $\pi_1$ ) and conventional manual instrumentation UKA ( $\pi_0$ ) groups.

The hypotheses are as follows:

- $H_0(\text{null})$ :  $\pi_1 \leq \pi_0$  versus
- $H_1(\text{alternate})$ :  $\pi_1 > \pi_0$ .

The proportions as described above will be supported with the use of a two-sided 95% confidence intervals (CI), estimated using exact binomial methods.

Superiority of  $\pi_1$  over  $\pi_0$  will be inferred if and only if the lower limit of the 95% CI for  $\pi_1$  is greater than the upper limit of the 95% CI for  $\pi_0$ .

As supportive analysis on the primary endpoint, the difference between the target and actual leg alignment achieved postoperatively will be summarized for each group (i.e. CORI UKA and the Conventional manual instrumentation UKA) using summary statistics for continuous variables. Ninety-five (95) % CIs based on the Student's t-distribution will be calculated for the means.

The primary endpoint and the supportive analysis will be summarized using the FAS analysis population as primary and then PP analysis population for sensitivity.

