## 11 SAMPLE SIZE JUSTIFICATION

Parratte et al.[51] looked at the effects of postoperative mechanical axis alignment on the survival of TKAs. They found that of the 398 TKAs reviewed in the paper there were 292 (73.4%) which post-operatively were defined as mechanically aligned (i.e. with a mechanical axis of  $0^\circ \pm 3^\circ$ ).

This study is designed to demonstrate superiority in the proportion of knees achieving post-operative leg alignment in the CORI Navigational group over the Conventional manual instrumentation group.

The proportion of mechanically aligned TKAs using NAVIO from a recent analysis was estimated to be 92.1% [52]. This proportion is expected to be equivalent if NAVIO was used to determine the proportion of mechanically aligned UKAs. Using these assumptions, enrollment of 63 UKAs per group will provide 80% power to show that the lower limit of the two-sided 95% confidence interval for the proportion of mechanically aligned UKAs is greater than that obtained from literature. To account for up to a 10% attrition rate in knees enrolled, 70 knees in each group (140 knees combined) will be enrolled into the randomized stage of the study. A minimum of an additional 5 subjects who will be treated with CORI directly to fulfil the learning needs of the surgeons will be enrolled at the pre-randomized study stage, thus leading to a minimum total study enrollment of 145 subjects.

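### The superiority rule (two separate exact 95% CIs must not overlap) is not the test that gives 63 per group; at the plan's own rates its power is 43–51%, not 80%.

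*Protocol*

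**What the plan says.** **Decision rule.** Protocol Section 10.4.1 tests whether the aligned proportion at 6 weeks is higher with CORI (π1) than with conventional instruments (π0). Each arm gets its own two-sided 95% "confidence intervals (CI), estimated using exact binomial methods". Superiority "will be inferred if and only if the lower limit of the 95% CI for" π1 lies above the upper limit of the interval for π0. No other test of the primary endpoint is given.

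**Significance level.** Section 10.1 states that, unless otherwise stated, "all significance tests and hypothesis testing will be two-sided, performed at the 5% significance level".

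**Sample size.** Section 11 says the aim is superiority over the conventional arm, but its power statement reads "enrollment of 63 UKAs per group will provide 80% power to show that the lower limit of the two-sided 95% confidence interval". The threshold that this limit has to clear is a published rate, not the control arm: "for the proportion of mechanically aligned UKAs is greater than that obtained from literature". That sets one interval against a fixed number. The control rate is from a published total knee series, in which "there were 292 (73.4%) which post-operatively were defined as mechanically aligned". For the test arm: "The proportion of mechanically aligned TKAs using NAVIO from a recent analysis was estimated to be 92.1" per cent. Allowing 10% attrition gives 70 per group.

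**SAP.** Section 6.1 repeats the literature criterion but gives 92.1% as the literature value to beat, which in the protocol is the expected rate in the test arm. Sections 7.1 and 7.10 drop the planned analysis because the study ended with four subjects enrolled.

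**The concern.** The number of knees, the power statement and the decision rule describe different tests. Only the decision rule determines whether the trial succeeds, and no power was calculated for it.

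The direction of the error can be seen without enumeration. Two intervals fail to overlap roughly when the observed difference exceeds 1.96 × (SE1 + SE0). A 5% test of the difference needs only 1.96 × √(SE1² + SE0²). The first is always larger, so the rule demands a bigger observed effect than the stated significance level does.

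This is the trial's only confirmatory question. If the planning assumptions were exactly right, the trial would be about as likely to miss superiority as to show it. The rule also takes no account of site, although "a block (by investigational site) randomization schedule will be generated". That is a lesser point, and the power figures do not depend on it.

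**Working it through.** **Inputs.** p1 = 0.921 and p0 = 0.734 (Section 11); exact two-sided 95% intervals and the non-overlap rule (Section 10.4.1); two-sided 5% (Section 10.1); n = 63 evaluable or 70 enrolled per arm (Section 11).

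**Step 1: reproduce 63.** Two-sample test with pooled variance and no continuity correction:

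n = [1.960·√(2·p̄·q̄) + 0.8416·√(p1q1 + p0q0)]² / (p1 − p0)²

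- p̄ = (0.921 + 0.734)/2 = 0.8275, so 2·p̄·q̄ = 0.2855
- p1q1 + p0q0 = 0.0728 + 0.1952 = 0.2680
- n = (1.0472 + 0.4357)² / 0.187² = 2.199 / 0.03497 = 62.9, rounded up to 63; 63/0.9 = 70

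Variants do not give 63: unpooled 61, continuity-corrected 74, one-sided 50.

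**Step 2: test Section 11's own wording.** For one exact interval against 73.4%, the lower limit clears 73.4% when at least 54 of 63 knees are aligned. At p1 = 0.921 the probability of that is 97.5%, and power first passes 80% at n = 36. So 63 does not come from this criterion. On the SAP's version (beat 92.1% when the true rate is 92.1%), all 63 of 63 must be aligned: 0.921^63 = 0.6%.

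**Step 3: how much stricter non-overlap is.** With n = 63, SE1 = √(0.0728/63) = 0.0340 and SE0 = √(0.1952/63) = 0.0557.

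- Non-overlap: 1.96 × (0.0340 + 0.0557) = 17.6 points
- Test of the difference: 1.96 × √(0.0340² + 0.0557²) = 12.8 points

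The planned difference is 18.7 points, barely above the first threshold. Exact intervals are wider than this approximation, which raises the threshold further.

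**Step 4: exact power.** Take Clopper–Pearson limits for every possible count in each arm, then sum the joint binomial probability over all pairs that meet the rule.

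| Rule, at 92.1% v 73.4% | 63 per arm | 70 per arm |
|---|---|---|
| Non-overlap, exact CIs (Section 10.4.1) | 43.1% | 51.3% |
| Non-overlap, Wilson CIs | 51.3% | 59.0% |
| Pooled two-sample z, enumerated | 81.3% | 85.8% |
| Pooled two-sample z, normal formula | 80.1% | 84.1% |
| Fisher's exact test | 74.9% | 80.6% |

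The non-overlap rule reaches 80% at 111 evaluable knees per arm. Its one-sided type I error is 0.07–0.16% for common true rates from 50% to 92.1%.

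**Step 5: an example.** Observed 58/63 v 46/63 (92.1% v 73.0%) is almost exactly the planned effect. Fisher's p is 0.009. The exact intervals are 82.4–97.4% and 60.3–83.4%. They overlap, so superiority would be denied.

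**Step 6: missing data.** Section 10.4.1 counts missing primary data as failures. If 10% of 70 per arm are missing, the rates become 0.9 × 92.1 = 82.9% and 0.9 × 73.4 = 66.1%, and non-overlap power falls to about 25%.

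**The case against.** **The trial is over.** The SAP cancels the primary analysis, so the rule will never be applied to these data. That is correct, and the finding is therefore about the plan as designed. Early termination does not make the stated power right.

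**The power figure depends on the control rate.** The 73.4% comes from total knee surgery. Section 4.1 of the protocol cites 30–60% malalignment for conventional unicondylar surgery, that is, 40–70% aligned. At 63 per arm and 92.1% for CORI, the non-overlap rule has 60% power at a 70% control rate, 93% at 60% and over 99% at 50%, but 35% at 75%. This stands as a caution: 43–51% is the power under the plan's assumptions, not a known true power. But the 80% claim rests on those same assumptions.

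**The rule is conservative and does no harm.** It does not inflate false positives, and a sponsor may choose a strict criterion. Testing the difference instead would raise the actual one-sided error from about 0.15% to about 2.5%, which is a real relaxation in a study meant to support registration. However, 2.5% one-sided is what the two-sided 5% in Section 10.1 implies. Nothing in the documents says a stricter level was intended, and the size was not set for one. Keeping the rule and correcting the size or the power statement would also be coherent.

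**Site.** Section 8.2.1 uses site blocks to balance allocation, and no effect of ignoring site has been quantified. Stratifying by site is optional.

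**Conclusion.** The concern holds and must be fixed in the plan as designed. At 92.1% v 73.4%, with the exact intervals the protocol specifies, the sole superiority rule has 43% power with 63 evaluable knees per arm and 51% with 70, against the stated 80%. The upper figure needs complete data on all 70; with 10% missing counted as failures, power is about 25%. The conclusion does not hinge on the choice of exact intervals, since Wilson intervals give only 51% and 59%. It does rest on the protocol's own planning rates and would soften if the true control rate were well below 73.4%. No reported result is affected, because only listings for four subjects will be produced.

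**What to change.** 1. **Section 10.4.1.** Conclude superiority if the lower limit of the two-sided 95% CI for π1 − π0 is above 0, using a named method such as Miettinen–Nurminen. A Mantel–Haenszel version stratified by site is an option. Keep the two arm-wise exact intervals as description.
2. **Section 11.** State that 63 per group comes from the two-sided 5% pooled two-sample test of 92.1% v 73.4%, and remove the comparison with literature. Align SAP Section 6.1, where 92.1% is named as the value to beat.
3. **If non-overlap is kept.** Restate power as about 43% (63 evaluable) or 51% (70 evaluable), or plan for about 111 evaluable knees per arm, and give the power under the missing-as-failure rule.

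**Cost.** Changes 1 and 2 are wording only, with no extra patients or data. In a running study they would need a protocol amendment with signatory and ethics approval (Section 16). The type I error returns to the level stated in Section 10.1. Since this study has ended, the correction matters wherever the wording is reused.

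**What it does not repair.** Missing-as-failure also costs the two-sample test power. At 82.9% v 66.1% with 70 per arm, (0.1683 − 1.96 × 0.0737)/0.0723 = 0.33, or about 63% power. The attrition allowance should be worked out under that rule.

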### 3.3 LIST OF ABBREVIATIONS AND DEFINITIONS

Abbreviation	Definition
ADE	Adverse Device Effect(s)
AE	Adverse Event(s)
ACL	Anterior Cruciate Ligament
ANCOVA	Analysis of Covariance
A/P	Antero-posterior
ASADE	Anticipated Serious Adverse Device Effect
AVN	Avascular Necrosis
BMI	Body Mass Index
CAS	Computer-assisted navigation systems
CE	Conformité Européene
CI	Confidence Interval
CORI	REAL INTELLIGENCE™ CORI™
eCRF	Electronic Case Report Form(s)
CRO	Contract Research Organization
CTA	Clinical Trial Agreement
CV	Curriculum Vitae
DD	Device Deficiency(ies)
DMP	Data Management Plan
ECG	Electrocardiogram
EDC	Electronic Data Capture
EQ-5D-5L	Five-level EuroQol five-dimensional
FAS	Full Analysis Set Population
FDA	Food and Drug Administration
FJS-12	Forgotten Joint Score
FU	Follow-Up

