### 9.1.2 Screening/Pre-operative Visit

1. Obtain written informed consent from the subject as detailed in Section 7.5.  
----- ***Do not proceed until the consent has been obtained*** -----
2. Obtain demographic information and medical history, including information on all concomitant medications/therapies.
3. Screen the subject for protocol inclusion/exclusion criteria.
4. The eCRF will assign the subject a study number. The subject identification log shall be completed accordingly.
5. Instruct the subject on treatment procedures.
6. Collect radiographic images of the affected knee for evaluation of leg alignment (Standing weight bearing A/P long leg X-ray).
7. Collect the 2011 KSS score objective measures (joint alignment, instability, motions & symptoms).
8. Have the subject complete the 2011 KSS score subject questions.
9. Have the subject complete the OKS patient-reported outcome measure.
10. Have the subject complete the EQ-5D-5L patient-reported outcome measure.
11. The subject will be randomized to treatment group (CORI or Manual conventional instrumentation).
12. Subjects will be instructed to return for the Operation Visit on a scheduled date.

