### 10.2 ANALYSIS POPULATIONS

The following are the analysis populations:

- Enrolled Population: This is defined as subjects enrolled and/or randomized to either CORI or Conventional manual instrumentation groups. A total of 140 patients will be competitively enrolled and or/randomized in the study across all the sites including the sites in China.
- Safety Population (SAF): This is defined as all subjects who were treated for UKA (include non-randomized subjects in China as CORI is a pre-market

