#### CONFIDENTIAL AND PROPRIETARY

This document contains information that is confidential and proprietary to Smith & Nephew PLC and Smith & Nephew, Inc. and is intended for use only by Smith+Nephew and its manufacturer. It shall not be reproduced or copied in whole or in part, nor shall the contents be disclosed by any means without prior written permission from Smith+Nephew, nor shall anyone make any use of it that is contrary to the expressed or implied wishes of Smith+Nephew.

Clinical Protocol	Study Number: CORI.2019.06
A Prospective, Multi-center, Randomized Controlled Study to Evaluate the Safety and Effectiveness of REAL INTELLIGENCE™ CORI™ in unicondylar knee arthroplasty (UKA) Procedure	Version: 4.0-Master, 07 Sep 2022
	Page: 78 of 167

product in China) with the use of CORI or conventional manual instrumentation.

- Intent-to-Treat Population (ITT): The ITT population is a subset of the randomized population which is defined as subjects randomized to either CORI or conventional manual instrumentation groups who have at least one post-operative assessment on any of the effectiveness endpoints or health-related quality of life (HRQoL) endpoints. Data summarized on the ITT population will be based on the intervention the subject was randomized to receive which may be different from the intervention the subject actually received.
- Per-Protocol Population (PP): The PP population is a subset of subjects in the FAS population who do not have major protocol deviations and who satisfied all enrollment eligibility criteria. Major protocol deviations will include but not only restricted to subjects enrolled who do not satisfy the study entry eligibility criteria. All other criteria that will be categorized as major deviations will be formally classified on a case-by-case basis prior to the final study database lock.

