### 10.3 BASELINE DATA

All observations available prior to the operative date will be defined as baseline (or preoperative) data. All demographic and pre-operative characteristics data will be summarized at baseline. All demographic and baseline characteristics will be summarized using the enrolled SAF, ITT and PP analysis populations.

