#### CONFIDENTIAL AND PROPRIETARY

This document contains information that is confidential and proprietary to Smith & Nephew PLC and Smith & Nephew, Inc. and is intended for use only by Smith+Nephew and its manufacturer. It shall not be reproduced or copied in whole or in part, nor shall the contents be disclosed by any means without prior written permission from Smith+Nephew, nor shall anyone make any use of it that is contrary to the expressed or implied wishes of Smith+Nephew.  
 TMP-CD-05-01 Clinical Protocol - Device - Revision D; SOP-CD-05 Clinical Protocol

Clinical Protocol	Study Number: CORI.2019.06
A Prospective, Multi-center, Randomized Controlled Study to Evaluate the Safety and Effectiveness of REAL INTELLIGENCE™ CORI™ in unicondylar knee arthroplasty (UKA) Procedure	Version: 4.0-Master, 07 Sep 2022
	Page: 83 of 167

preoperative to postoperative visits will also be summarized. In the case of bilateral knees, repeated measures ANCOVA models will account for correlation between subjects with bilateral knees each for the index score and VAS analogous to that specified for the 2011 KSS will be used.

The 2011 KSS, transformed FJS-12 and EQ-5D-5L scores will additionally be summarized by group (i.e. the CORI Navigational and Conventional manual instrumentation groups) and visit using descriptive statistics for continuous variables.

The Multiple Imputation (MI) missing value imputation method will be used as the imputation method for missing 2011 KSS, FJS-12, OKS, and EQ-5D-5L endpoints. Details of the MI method will be included in the SAP.

All secondary endpoints will be summarized using the FAS analysis population.

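### The primary analysis set (FAS) is named but never defined, and Section 11's attrition allowance does not match the rule that scores missing primary results as failures

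*Protocol*

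**What the plan says.** **Analysis sets.** Protocol Section 10.4.1 makes FAS the main set for the primary endpoint: "The primary endpoint and the supportive analysis will be summarized using the FAS analysis population as primary". Section 10.4.2 adds "All secondary endpoints will be summarized using the FAS analysis population", and Section 10.4.3 uses FAS for the other endpoints. Section 10.2 also builds the per-protocol set on it: "The PP population is a subset of subjects in the FAS population". The only expansion is in the abbreviation list, "Full Analysis Set Population", where ITT has its own entry.

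Section 10.2 defines four sets: Enrolled, SAF, ITT and PP. Enrolled reads "This is defined as subjects enrolled and/or randomized to either CORI or Conventional manual instrumentation groups". ITT takes randomised subjects "who have at least one post-operative assessment on any of the effectiveness endpoints" or on a quality-of-life endpoint, analysed as randomised. Section 10.3 says baseline data "will be summarized using the enrolled SAF, ITT and PP analysis populations", naming ITT where FAS might be expected. SAP 7.2 is marked not applicable and refers back to the protocol's populations. SAP 7.3, on missing data, is also not applicable.

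**Timing and labels.** Section 9.1.2, step 11, reads "The subject will be randomized to treatment group (CORI or Manual conventional instrumentation)". That visit falls within 90 days before surgery (Table 9.1.1-9-1), and Section 8.2.2 says the trial is not blinded. Section 7.6 classes any consented but untreated subject as a screen failure, whatever the reason. Section 9.1.3 gives the same label to a subject found ineligible before surgery. Section 7.8.1 calls stopping close to or during surgery a withdrawal from treatment.

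**Attrition and missing data.** Section 11 takes 63 knees per group to 70 for attrition of up to 10%. Section 10.4.1 treats every missing primary result as a failure, and Section 7.8.2 says withdrawn subjects are not replaced.

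**The concern.** Two candidate meanings of FAS give different denominators. If it means the written ITT, a randomised subject with no post-operative assessment drops out. If it means all randomised subjects, that subject stays and is scored a failure. The text does not choose.

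The conflicting labels feed the same question. A subject randomised at the pre-operative visit and then not operated on could be recorded as a screen failure or as withdrawn from treatment, and staff know the allocation by then. Under the written ITT rule such a subject leaves the analysis under either label, for lack of a post-operative assessment.

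The choice of set also decides whether Section 11's allowance works. Dividing by 0.9 restores 63 evaluable knees only if lost subjects leave the denominator. The missing-as-failure rule acts on subjects inside the set. The two provisions are therefore compatible only for subjects who fall outside the analysis set. Anyone inside it without a 6-week result lowers the success rate in their arm and shrinks the expected difference.

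**Working it through.** **Inputs.** Success rates 0.921 (CORI, from the predecessor system) and 0.734 (historical, 292/398), 80% power, 63 raised to 70 per group: Section 11. Two-sided 5% level: Section 10.1. Missing scored as failure: Section 10.4.1.

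**Reproducing the plan's figure.** The two-sided, pooled-variance formula for two proportions, without continuity correction, is

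n = [1.960·√(2p̄(1−p̄)) + 0.842·√(p₁(1−p₁)+p₀(1−p₀))]² / (p₁−p₀)²

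With p̄ = 0.8275 the square roots are 0.5343 and 0.5177, so n = (1.0472 + 0.4357)² / 0.187² = 62.9, which rounds up to 63. Then 63/0.9 = 70. Both planned figures reproduce.

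**Power when missing results are handled differently.** Let n be the number per arm kept in the set and f the fraction of those with a result. Scored rates are 0.921f and 0.734f, and

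power = Φ{[(p₁−p₀)√n − 1.960·√(2p̄(1−p̄))] / √(p₁(1−p₁)+p₀(1−p₀))}

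evaluated at the scored rates. Missingness is assumed equal in both arms and unrelated to alignment.

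| Case, per arm | n | f | Scored rates | Power |
|---|---|---|---|---|
| None missing | 70 | 1 | 0.921 v 0.734 | 84.1% |
| 7 missing, all leave the set | 63 | 1 | 0.921 v 0.734 | 80.1% |
| 7 missing, 4 leave, 3 scored failures | 66 | 63/66 | 0.879 v 0.701 | 71.6% |
| 7 missing, all scored failures | 70 | 0.90 | 0.829 v 0.661 | 62.9% |
| 5% missing, all scored failures | 70 | 0.95 | 0.875 v 0.697 | 73.2% |
| 1 missing, scored failure | 70 | 69/70 | 0.908 v 0.724 | 81.0% |

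For the 62.9% row: (0.1683 × √70 − 1.960 × 0.6166) / 0.6050 = 0.330, and Φ(0.330) = 0.629.

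**Sensitivity to how the test is read.** Section 11's wording describes a CORI lower limit set against a literature value, and Section 10.4.1 requires non-overlapping exact intervals. Exact binomial calculation of the three 7-missing cases, in the table's order, gives 97.5%, 83.1% and 45.4% on the first reading (taking 73.4% as the literature value), with 84.0% at 5% scored failures. On the second it gives 43.1%, 33.4% and 25.2%, against 51.3% with none missing. Power falls on every reading, but by different amounts. The low starting value under the non-overlap rule is a separate problem.

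**The case against.** The strongest reply is that FAS is simply another name for ITT. Section 10.3 lists ITT alongside SAF and PP, and ITT has a written rule. On that reading Sections 11 and 10.4.1 can coexist: subjects never assessed after surgery leave the set, and the missing-as-failure rule covers those assessed but lacking the film. This is plausible, but no sentence says it, the abbreviation list carries both terms, and subjects assessed without a film would still cost power. The 10% is also an upper bound with no visit attached in a 12-month study, so loss by 6 weeks could be well below it. That stands, and it is why a range is shown.

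A reader might go further in four ways that the documents do not support.

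- **That 80% power survives only if every missing subject leaves the set.** One scored failure per arm still gives 81.0%, and the literal one-sample reading gives 83.1% to 84.0% in the intermediate cases.
- **That relabelling a subject as a screen failure removes them from the analysis.** No set is defined by that label, and the Enrolled definition includes randomised subjects.
- **That 63 or 70 is miscalculated.** Neither is.
- **That scoring missing results as failures is not conservative.** Under the non-overlap rule, false superiority is at most 0.2% when 0, 5 or 10% are missing equally, for true rates from 73.4% to 92.1%. It exceeds 2.5% only in an assumed extreme (none missing in CORI, 10% in control, true rates of 80% or more). This deserves a one-line qualifier at most.

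**Conclusion.** The point holds as a minor defect of definition and consistency. FAS has no membership rule in either document, and the labels for randomised but untreated subjects conflict. The stated 80% power with up to 10% attrition is not delivered, on the pooled formula behind the 63, unless almost all missing subjects fall outside the analysis set. At the 10% ceiling, power lies between 62.9% and 80.1% depending on how many leave.

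These figures assume equal missingness in the two arms, unrelated to outcome, and a total of 70 per arm. Section 7.6 counts only treated subjects as enrolled. If the 70 are treated subjects, an all-randomised set would add untreated subjects beyond 70, each scored a failure, and the table does not include them.

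No current inference changes. SAP Section 2 records termination with four subjects, and SAP 7.1 replaces the planned analyses with listings. The point matters if the design is reused, and in one small way now: SAP 7.2 relies on listings from which the protocol's populations can be identified, which is not possible for a set with no rule.

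**What to change.** If the protocol is reissued or its design reused:

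- **Section 10.2:** define FAS as all randomised subjects, analysed as randomised, and use that one name in Sections 10.3 and 10.4.
- **Sections 7.6 and 9.1.3:** limit the screen-failure label to subjects not yet randomised, reconcile it with Section 7.8.1, and report randomised but untreated subjects by arm with the reason.
- **Section 11:** restate power with missing results scored as failures, under the decision rule actually used, for a stated range of 6-week missingness that includes randomised but untreated subjects. Enrolment need not rise. The cost is that stated power falls below 80% when missing films are scored as failures at about the planned rate.
- **Section 10.4.1 (optional):** add that the missing-data rule is conservative when missingness is similar in both arms.

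If the protocol is not reissued, a short note in SAP 7.2 and 7.15 is enough, with three listing columns: randomised arm, treated yes/no, and 6-week film yes/no. Neither route adds subjects or visits.
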